##### *Rectal temperature probes:*

The use of rectal probes to measure core temperature carries minimal risk. The primary risk is of damage to the lining of the rectum; however, this risk is very slight as we use a flexible thermistor that is designed for this

purpose. We will exclude any subjects who have had recent rectal, anal, vaginal, or prostate surgery. In addition, we will exclude any subjects who have a personal history of heart disease, as the use of a rectal thermometer can cause a vagal reaction, increasing the potential for arrhythmias and fainting. There is also the risk of infection, either by the subject not washing their hands properly or exposure by others to a poorly cleaned probe. We will use clean, sterile disposable probes to minimize this risk. The risk of infection is similar to that of having a bowel movement, and is considered minimal (similar to daily experience). There is also the risk of embarrassment. The approach is typically well tolerated by subjects, and the investigative team is professional in regard to their treatment of the subjects.

### **Recruitment:**

Participants will be recruited for this study through IRB-approved flyers posted at the University of Kansas Medical Center, in the community, and through electronic communications via websites and email. The study team will also utilize the Pioneers/Frontiers Research Participant Registry after approval from the Data Request Committee (DRC). Individual mailings and phone calls will be made to applicable subjects from the Pioneer/Frontiers Research Participant Registry.

### *Vulnerable Populations:*

The recruitment plan will not include any of the vulnerable groups below, except possible students or employees of the University or Health System:

- I. Cognitively or decisionally impaired individuals
- II. Children
- III. Pregnant women
- IV. Prisoners
- V. Students and/or employees: While our study does not specifically seek to recruit this subgroup, it is not outside the realm of possibility that students or employees may contact the study team after having seen recruitment postings or if they have previously consented to participate in the Pioneers/Frontiers research registry.

### **Assessment of Subject Safety and Development of a Data and Safety Monitoring Plan:**

Nursing and study staff will continually monitor participants for adverse events. Any adverse event will be immediately reported to the PI and study coordinator per KUMC Human Subject Committee reporting policies. This procedure will be scheduled when a CTSU safety monitor is available. The Principal investigator will assess safety data after every 5 subjects are enrolled. If a trend of adverse events related to heat-related illness occurs, the study will pause or stop until the safety issue is assessed and addressed by the study team.

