### *Hot Water Immersion Therapy*

Previous reports have demonstrated that benefits from heat therapy require 5-14 days to become apparent. Thus, participants in the present study will undergo 8-10 shoulder-high hot water immersions of 40.5°C for 45 minutes/session during a 14-16-day period. Either 1) a rectal probe with sterile disposable sheaths or 2) a sterile rectal thermistor probe will be used to monitor the subject's temperature ( $T_{re}$ ). These probes are inserted approximately 2.54 cm past the anal sphincter. The subject will be removed from the hot tub if  $T_{re}$  is 38.5°C or higher. Participants will be asked to sit on a bench of the hot tub with until  $T_{re}$  is < 38.0°C at which time they may return to the hot tub. Participants are able to drink water *ad libitum* while in the hot tub.  $T_{re}$  will be monitored for 10 additional minutes following emersion from the hot tub or until  $T_{re}$  < 38.0°C.

Hot tub located in the CRC at KUMC.

Subjects will have dry weights measured prior to and after hot water therapy. If body weight loss following therapy is > 1%, the participant will be asked to drink additional fluids to make up the difference. Heart rate will be monitored continuously during heat therapy. If heart rate is altered > 50% from baseline, the participant will

be assessed for neurologic and hemodynamic changes. If there are changes concerning these assessments, the subject will be removed from the hot tub, temperature monitored, and a medical provider notified. Blood pressure will be obtained prior to and after hot water therapy. Participants with pre-therapy systolic blood pressure < 75mmHg or > 180mmHg and/or diastolic blood pressure < 40mmHg or > 90mmHg, will not be allowed to participate in hot water therapy. If post-hot tub blood pressure varies by > 20% lower or > 30% higher than baseline values, the subject will be monitored until return to < 20% deviation from baseline. If blood pressure values do not return to baseline after 10 minutes, discussion with a medical provider will take place prior to discharge from CTSU. If at any time, should a participant become hemodynamically or cognitively impaired during any portion of the study activities, 911 will be called for evaluation and possible transport to the emergency department at TUKH.

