#### *Cardiovascular performance: Oxygen consumption measurements*

Study participants will complete the treadmill exercise respirometry at their first study visit. This exercise will also be performed on within 24 to 48 hours of the final hot tub experience. This waiting period will obviate the transient enhancements of cardiac output and systemic vascular resistance due to water immersion that may alter  $VO_{2max}$  assessments. These effects are normalized shortly after removal from the water and heat sources, thus should be normalized and not have impact on  $VO_{2max}$  by this time. This waiting period also allows for muscle rest prior to the exercise step test. Importantly, waiting until the next day to perform the laboratory and exercise testing also ensures that the changes seen are not acute benefits of heat therapy, but are chronic.

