#### **Risks:**

##### *Whole-Body Heat Therapy:*

There are some risks associated with heat exposure, including: fatigue, light-headedness, muscle cramps, dehydration, and neurological detriments (i.e. heat stroke). However, these symptoms do not typically occur until core temperature rises above 40°C. Core temperature (rectal thermistor) will be continuously monitored and recorded. Subjects will be removed from the hot bath immediately if either core temperature reaches 39.5°C or the subjects experience any symptoms of heat-related illness. All symptoms subside upon lowering core temperature. Ice packs will be on hand if rapid cooling is necessary (see Rapid Cooling SOP). Heart rate will also be continuously monitored and recorded throughout heating. If HR increases > 60 beats/min above resting or increases > 20 beat/min with a 5 min time period, subjects will be moved to a seated position if they were previously fully submerged, or removed from the hot tub if they were already sitting up. Additionally, heat exposure may have detrimental effect on a developing fetus in females. Thus, subjects who are pregnant or trying to conceive will be excluded from the study. This will be confirmed with a pregnancy test.

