### *Definition of Adverse Experiences:*

Adverse events are defined as any untoward medical occurrence in study participants or others, which does not necessarily have to be a causal relationship with the study treatment. The seriousness of the adverse event will be determined using the National Cancer Institute Common Terminology Criteria for Adverse Events (CTCAE) v3.0, Adverse events (AE) will be reported if they are reported by the patient or observed by research staff to cause a noticeably different experience than is typical for the individual (CTCAE v3 Grade 1-2) Serious adverse events (SAE) will be deemed those AEs significant enough to interfere with activities of daily living (CTCAE v3 Grade 3-5). An adverse event in any category rated 3 or greater according to CTCAE v3.0, will result in immediate termination of the procedure.

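### The only study-level pause trigger is a trend of heat-related illness, so one related Grade 4-5 event, or repeated probe or treadmill events, does not require a pause

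*Protocol*

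**What the plan says.** The study-level rule is in the Protocol, Assessment of Subject Safety and Development of a Data and Safety Monitoring Plan: "If a trend of adverse events related to heat-related illness occurs, the study will pause or stop until the safety issue is assessed". The same section says "Any adverse event will be immediately reported to the PI and study coordinator per KUMC Human Subject Committee reporting policies", and has the principal investigator look at safety data after every 5 participants enrolled.

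The participant-level rule for severe events is under Definition of Adverse Experiences: "An adverse event in any category rated 3 or greater according to CTCAE v3.0, will result in immediate termination of the procedure". That section classes Grades 3 to 5 as serious and does not require an adverse event to be caused by the study treatment.

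The protocol's own account of risk is wider than heat. Under Whole-Body Heat Therapy it lists "neurological detriments (i.e. heat stroke"). Under Rectal temperature probes it says "The primary risk is of damage to the lining of the rectum", adds "There is also the risk of infection", and mentions a vagal reaction that can lead to arrhythmia and fainting. There is also an exercise test: "Study participants will complete the treadmill exercise respirometry at their first study visit", repeated 24 to 48 hours after the last immersion. On exposure, "participants in the present study will undergo 8-10 shoulder-high hot water immersions", each of 45 minutes, and 20 adults aged 50 or older are planned.

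**The concern.** A pause rule settles in advance what happens when something serious occurs, so that the decision is not improvised afterwards. This rule has two conditions, and each excludes cases that matter.

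- **Trend.** On a plain reading, one event is not a trend. A single related life-threatening or fatal event does not meet the rule, even if it is heat stroke, which the protocol lists as a risk.
- **Heat-related illness.** Rectal injury, infection or a vagal arrhythmia from the probe is not heat-related illness, and neither is an event on the treadmill. However often these recur, the rule is not met.

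In either case, whether other participants go on being immersed and tested while the cause is examined depends on the investigator's discretion and on committee policies outside this document.

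A smaller point concerns the Grade 3+ rule. It does not say whether the procedure it ends is the activity under way or the participant's whole course, nor who decides whether the participant resumes.

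**Working it through.** The safety rule contains no event rate, count or threshold, so there is no figure in the plan to reproduce. The check is first of the text, then of exposure.

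**Step 1. Every stop statement in the protocol, and what it acts on**

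| Section | Condition | Acts on |
|---|---|---|
| Study Cohort and Safety | Hemodynamic or cognitive impairment: emergency call | Individual |
| Hot Water Immersion Therapy | Rectal temperature or heart-rate limits; blood pressure out of range; medical provider notified or consulted in set cases | Individual |
| Whole-Body Heat Therapy | Temperature limit, heat symptoms or heart-rate limits: moved or removed from the tub | Individual |
| Definition of Adverse Experiences | Any Grade 3+ event: ends the procedure | Individual |
| Safety monitoring plan | Trend of heat-related illness: pause or stop | Study |

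Only the last row acts on the study.

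**Step 2. Test cases against that row**

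- One related Grade 4-5 heat stroke: heat-related, but not a trend. No pause required.
- One related Grade 4-5 arrhythmia from the probe: neither condition met. No pause required.
- Several probe injuries or infections, or several treadmill events: perhaps a trend, but not heat-related illness. No pause required.

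**Step 3. Exposure left without a required pause**

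Inputs: 20 participants, 8 to 10 immersions each, 2 treadmill tests each (start and end). Assumptions: participants are treated one after another and complete the course. The protocol states no such schedule.

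Total planned: 20 × 8 = 160 to 20 × 10 = 200 immersions.

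For an event in participant k, others still to come: (20 − k) × 8 to (20 − k) × 10 immersions and (20 − k) × 2 tests.

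- k = 1: 19 × 8 = 152 to 19 × 10 = 190 immersions; 19 × 2 = 38 tests.
- k = 10: 10 × 8 = 80 to 10 × 10 = 100 immersions; 10 × 2 = 20 tests.
- k = 20: none.

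For the affected participant, a Grade 3+ event in session 1 leaves 8 − 1 = 7 to 10 − 1 = 9 immersions (7 × 45 min = 5.25 h to 9 × 45 min = 6.75 h) if only the activity under way ends, and 0 if the whole course ends.

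**Step 4. Illustration of one event versus a trend**

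The protocol gives no event rate. Assume a per-participant rate p of a related severe event, independent across 20 participants, and take two events as the fewest that could be called a trend.

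P(at least 1) = 1 − (1 − p)^20; P(at least 2) = P(at least 1) − 20p(1 − p)^19.

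| Assumed p | At least 1 | At least 2 | Exactly 1 (difference) |
|---|---|---|---|
| 1% | 0.1821 | 0.0169 | 0.1652 |
| 2% | 0.3324 | 0.0599 | 0.2725 |
| 5% | 0.6415 | 0.2642 | 0.3773 |
| 10% | 0.8784 | 0.6083 | 0.2701 |

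Across this assumed range, the chance that the trial sees exactly one such event, and so never reaches a trend, is about 0.17 to 0.38. The table describes how the rule behaves; it is not a forecast.

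**The case against.** The strongest reply is that the rule is a sufficient condition, not an exclusive one. It says when the study will pause and nowhere bars a pause for another reason. The principal investigator is told of every event immediately, under committee policies that may themselves require a halt. Reviews fall due at 5, 10, 15 and 20 enrolled, and a safety monitor's availability is a condition of scheduling. Heat stroke lies behind several individual stops: temperature and heart-rate limits, removal at any heat symptom, and cooling supplies at hand. The protocol calls the probe risk minimal, names no treadmill harm, and lets participants rest during exercise.

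Much of this stands. A reader might infer that the protocol lets the trial run on after a death, or that nobody would be watching. The documents support neither: silence is not permission, and the reporting chain is immediate. A reader might also take 152-190 immersions as the harm at stake. That figure is only the planned sample less the first participant, under an assumed schedule, and it supposes that nobody intervenes at any review.

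The ambiguity over the procedure is also modest. The natural reading is the activity under way. The monitoring section speaks of a procedure as something scheduled and of the study as what pauses, so reading the Grade 3+ rule as ending the whole study has no support. What is missing there is a rule on resumption.

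The reply does not show any written requirement to pause in the Step 2 cases. The individual stops protect the person affected, and the reporting duty informs the investigator. Neither obliges anyone to hold the next immersion. Since the protocol chose to write a study-level rule, its narrow scope is a fair criticism.

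**Conclusion.** The point holds as a trigger drawn too narrowly. As written, neither a single related Grade 4-5 event nor repeated related probe or treadmill events requires the study to pause. The probe case is the firmer of the two, because the protocol itself names those harms; the treadmill case rests only on the test being performed.

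The size is bounded, not estimated. At most 152-190 immersions and 38 treadmill tests in 19 others would follow an event in the first participant with no required pause, falling to none by the twentieth. This assumes one-after-another treatment, full completion and no discretionary or committee-imposed pause. Overlapping enrolment would change the counts.

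The conclusion depends on the protocol text alone; the committee policies are not shown and could narrow the gap in practice. The wording of the Grade 3+ rule is a minor clarification. The trigger should be amended, but this is not evidence that oversight is missing.

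**What to change.** **Safety monitoring section.** Keep the heat-illness trend and add two countable triggers. Enrolment and immersions pause pending review after:

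- any single Grade 4-5 event at least possibly related to a study procedure (immersion, rectal probe or treadmill test); or
- two or more related Grade 3 events of the same kind.

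**Definition of Adverse Experiences (minor).** State that a Grade 3+ event ends the activity under way and that, if the event is related, the participant's further immersions are suspended until a medical provider clears them. The limit to related events matters because the protocol's definition of an adverse event does not require causality; without it, an unrelated illness would also suspend treatment.

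**Cost.** The text changes are confined to these two sections. In operation, the cost is an occasional pause, or a participant with fewer than 8 sessions. Under the assumed rates in the working, now taken as rates of related Grade 4-5 events, the single-event trigger would be met at least once in 20 participants with probability 0.18 at 1% and 0.33 at 2%. That is acceptable in a pilot of this size, where each such pause would follow a life-threatening or fatal event.

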### *Definition of Adverse Experiences:*

Adverse events are defined as any untoward medical occurrence in study participants or others, which does not necessarily have to be a causal relationship with the study treatment. The seriousness of the adverse event will be determined using the National Cancer Institute Common Terminology Criteria for Adverse Events (CTCAE) v3.0, Adverse events (AE) will be reported if they are reported by the patient or observed by research staff to cause a noticeably different experience than is typical for the individual (CTCAE v3 Grade 1-2) Serious adverse events (SAE) will be deemed those AEs significant enough to interfere with activities of daily living (CTCAE v3 Grade 3-5). An adverse event in any category rated 3 or greater according to CTCAE v3.0, will result in immediate termination of the procedure.

### *Expected Adverse Experiences:*

Expected adverse experiences include potential bruising and soreness at the site of blood draw.

### **Data Protection:**

All data will be deidentified by giving participants a random number that will be unable to be traced to identity or demographic data. All data will be stored in a database on the PI's password protected, hospital computer in a password protected spreadsheet. This computer is housed in a locked hospital office.

### *Objectives*

The main objective of this pilot study is to understand the relationship between the molecular mechanisms of cardiovascular improvements demonstrated in previous studies due to heat therapy to functional cardiovascular improvements in humans. The translation of enhanced endothelial arterial distensibility into improved oxygen consumption, or  $VO_{2max}$ , has yet to be studied. If indeed, the benefits of heat therapy do translate into better cardiovascular health, the implications of this would be far reaching for millions of people who suffer from cardiovascular disease throughout the world.

The current pilot study will measure cardiovascular function following hot water therapy in patients without significant cardiovascular disease. However, the findings of this study will hopefully set the framework for hot water therapy in patients with NYHA Class II -III heart failure in a future study. The benefits in these patients may not only be in  $VO_{2max}$  and biomarker measurements of cardiac function improvements, but also in activities of daily living. This would have a very meaningful impact on society due to the large and ever-increasing number of patients with heart failure. Currently the National Institute of Health recognizes heart failure as major public health problem with a prevalence over 5.8 million Americans and 23 million people worldwide. Heart failure has been singled out as an emerging epidemic. Furthermore, the need for research is increasing as each year more than 550,000 new cases of heart failure are diagnosed in the United States.

Importantly, the amount of healthcare expenditure on heart failure is staggering. More than one million hospitalizations for heart failure occur yearly. Additionally, commonly prescribed medications to treat the symptoms associated with this disease are expensive and many are not covered by major health insurance companies.

Ultimately, with results from this and other pilot studies, the breadth of knowledge in this field of endothelial translational research will dramatically increase. However, it is necessary to continue the pursuit of understanding heat therapy and the implications in patients with cardiovascular disease. Unlike other morbid disease processes, heart failure can often be prevented and treated such that patients live higher quality lives. This in turn, allows freedom from hospital admission and costly medications. Utilizing the human body's own molecular mechanisms to combat cardiovascular disease is the ideal prevention and therapeutic strategy. We believe heat therapy will be an important stepping stone in understanding these molecular pathways and possibly in treating cardiovascular disease.

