### Study Aim:

#### *Translation of Endothelial Modifications using Heat Therapy into Cardiovascular Fitness Improvement*

In this study, we will assess if the reported improvements in endothelial function translate into improved cardiovascular function. Since heat therapy has been shown to illicit several molecular markers of benefit for endothelial function including enhancement of FMD and other markers of arterial distensibility, there is a potential direct benefit for cardiovascular health and fitness. As of today, these benefits remain theoretical.

Improvements in cardiovascular function are measured by increased exercise tolerance with various strategies of fitness testing. Historically, the gold standard of fitness testing relies on measurements of maximal oxygen consumption ( $VO_{2max}$ ). There are numerous methods to obtaining  $VO_{2max}$ , however some methods are invasive, require significant equipment and/or require intense exercise by the participant. The methods chosen for this study are validated, utilize two different mechanisms of  $VO_{2max}$  measurements in order to enhance reliability, are noninvasive and require minimal exercise in which the participant can rest when needed to ensure safety.

Oxygen consumption testing ( $VO_2$ ) will be measured with a treadmill exercise respirometry study. This test measures  $VO_2$  indirectly by measuring energy expenditure. This method is known as indirect calorimetry and is the gold standard for measuring energy expenditure. Study participants will complete the treadmill exercise respirometry on the day of their first hot tub immersion, prior to the hot tub session. This exercise will also be performed on within 24 to 48 hours of the final hot tub experience.

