### *Study Cohort and Safety*

Twenty adults, age 50 or older, will be included in the study. Demographic data required for pertinent calculations will be obtained from each participant including height, weight, age and gender. Exclusion criteria includes current major cardiovascular disease known to the patient including recent myocardial infarction, stroke, angina pectoris, high grade coronary vasculopathy or atherosclerosis, severe valvular disease, current cardiac dysrhythmia that requires treatment (i.e. atrial fibrillation, atrial flutter, frequent ventricular premature beats and/or implantation of permanent pacemaker/defibrillator). Patients with a history of coronary artery bypass grafting, valvular surgeries and coronary interventions will be assessed as to current exercise tolerance and symptomology. Other exclusion criteria include current treatment with steroids or immunosuppressive agents, current malignancy, serious liver disease, end-stage renal disease or judgement by a medical provider that water or heat therapy poses an undue burden or risk upon the individual. All females of child bearing age will consent to pregnancy testing and will be excluded if pregnant. Should a participant become hemodynamically or cognitively impaired during any portion of the study activities, 911 will be called for evaluation and possible transport to the emergency department at TUKH. Volunteers can choose to recuse themselves from any or all of the study activities at any time.

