#### **Measurements:**

The following data will be collected at two separate time points: T1 = beginning of the study, prior to hot water immersion; and T2 = at the end of the study, 24-48 hours after the last hot tub experience.

1. Blood pressure, stroke volume, stroke volume variation, cardiac index and systemic vascular resistance, heart rate with the ClearSight® (Edwards Lifesciences, Irvine, CA) monitor
2.  $VO_2$  as measured with treadmill exercise respirometry
3. Blood collection tube of approximately 4 tablespoons of blood to assess complete blood count, complete metabolic panel, lipid panel, and serum heat shock protein measurements (Hsp72 and Hsp90)

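### The 24-48 hour wait can rule out acute immersion effects only; one treated arm with one treadmill test before and one after cannot attribute a VO2 change to heat.

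*Protocol*

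**What the plan says.** The aim, in the Protocol's Study Aim section, is causal in form: "we will assess if the reported improvements in endothelial function translate into improved cardiovascular function". The Objectives section names translation into improved VO2max as the unstudied question and adds "If indeed, the benefits of heat therapy do translate into better cardiovascular health, the implications of this would be far reaching".

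The design is fixed in four places:

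- **Study Cohort and Safety:** "Twenty adults, age 50 or older, will be included in the study".
- **Hot Water Immersion Therapy:** "participants in the present study will undergo 8-10 shoulder-high hot water immersions of 40.5°C for 45 minutes/session during a 14-16-day period". No other group is described.
- **Measurements:** "The following data will be collected at two separate time points: T1 = beginning of the study, prior to hot water immersion", and then "T2 = at the end of the study, 24-48 hours after the last hot tub experience".
- **Cardiovascular performance: Oxygen consumption measurements:** "Study participants will complete the treadmill exercise respirometry at their first study visit". The second test follows 24-48 hours after the last session.

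That last section gives the reasons for the wait: circulatory effects of immersion settle, muscles rest, and the observed changes can then be taken as chronic rather than acute benefits of heat. The Study Aim section adds that the chosen tests need little exercise and let participants rest when necessary.

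**The concern.** The sentence on the wait leaves one question open, whether the benefit is transient or lasting, and treats the cause of the change as known. The only rival explanation the protocol considers is the acute effect of immersion.

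Three others are not mentioned. T1 is the participant's first treadmill test in the study and T2 the second, so familiarity may raise the result. How hard and how long a participant works is partly voluntary, and everyone knows they have completed the heat series. Fitness, activity and equipment may also drift over 14-16 days.

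At stake is what the trial may conclude. The Objectives section hopes the findings will frame a study in NYHA Class II-III heart failure. A change read as a heat effect would enter that planning as evidence of efficacy, although the design could produce the same change without heat doing anything. No analysis plan can repair this, because the missing information was never collected.

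**Working it through.** The protocol states no effect size, SD, significance level or power, so there is no figure to reproduce. The main check is what the design can identify.

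**1. What T2 − T1 contains.** For treadmill VO2, write the expected change as

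E(T2 − T1) = Hₐ + H_c + L + F + D,

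with Hₐ the acute immersion effect, H_c the lasting heat effect, L test familiarity, F a change in effort or expectation, and D drift.

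**2. What the wait does.** If immersion effects have settled by 24-48 hours, as the protocol argues, Hₐ ≈ 0. What is left is H_c + L + F + D. The last three do not fade with time out of the water, so the wait does not remove them.

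**3. What can be estimated.** One arm with two time points gives one mean change for four unknown terms. H_c can be recovered only by assuming L + F + D = 0, and the protocol provides nothing to check this: no practice test, repeat baseline, unheated interval or comparator. As n grows, the confidence interval narrows around the sum, not around H_c. More participants in the same arm therefore make false attribution more likely.

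**4. Illustration of size.** Only n = 20 comes from the protocol. Assumed: true heat effect zero, two-sided paired t-test at 5%, baseline VO2 of 25 mL/kg/min, a non-heat gain of 0%, 2%, 4% or 5% (0, 0.5, 1.0 or 1.25 mL/kg/min), and SD of the change of 2 or 3. The noncentrality is gain / (SD/√20), with df = 19.

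| Assumed gain (mL/kg/min) | SD 2: noncentrality | SD 2: P(significant) | SD 3: noncentrality | SD 3: P(significant) |
|---|---|---|---|---|
| 0 | 0 | 0.050 | 0 | 0.050 |
| 0.5 | 1.12 | 0.186 | 0.75 | 0.109 |
| 1.0 | 2.24 | 0.565 | 1.49 | 0.294 |
| 1.25 | 2.80 | 0.755 | 1.86 | 0.424 |

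The range runs from no inflation to a large one, and the documents do not say where this trial would lie.

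**5. What a delayed-start comparison within the same 20 would give.** Ten participants would repeat the T1 tests after an unheated 14-16 days.

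- 95% half-width for the repeat-test effect: 2.262 × 2/√10 = 1.43 mL/kg/min at SD 2, and 2.262 × 3/√10 = 2.15 at SD 3. Both exceed the largest gain assumed above.
- 95% half-width for the 10:10 contrast at SD 2: 2.101 × 2 × √(1/10 + 1/10) = 1.88 mL/kg/min.
- Power of the 10:10 contrast for a heat effect of half an SD of the change: 18.5%.

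**The case against.** The protocol is more cautious than one sentence suggests. It calls itself a pilot, describes the fitness benefits as so far theoretical, only hopes to frame a later study, and says further work is needed. A one-arm before-and-after pilot is a legitimate choice. This stands, and it limits the point to a correction of wording. It does not remove the point: the protocol sets no feasibility or variance-estimation aim in place of the functional question, and none of its cautions says that a change might not be due to heat.

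A reader might be tempted to go further in four ways that the documents do not support:

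- **That the Objectives section declares any gain a benefit of heat.** The sentence there is conditional. The attribution lies in the explanation of the wait.
- **That regression to the mean inflates the change.** This shifts a group mean when people are selected on an extreme baseline. Entry here depends on age and health status, with no VO2 or fitness threshold. The blood-pressure limits govern access to the hot tub and are not VO2 criteria.
- **That every outcome is equally exposed.** Lipids, Hsp72 and Hsp90 are not plausibly moved by treadmill practice or effort. They too lack a comparator, but the argument about familiarity and effort concerns treadmill VO2.
- **That the false-positive rate is 56% or 75%.** These figures follow from assumed inputs and an assumed test. They show direction, not an expected rate.

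**Conclusion.** The concern holds for treadmill VO2 and for what the protocol says the wait establishes. The wait can support a statement that a change is not an acute immersion effect. It cannot support a statement that the change is due to heat, because familiarity, effort and drift remain in the same difference.

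This conclusion rests only on the design the protocol fixes: one treated arm, one test before, one after, no familiarisation test and no comparator. It needs no assumed figure. Its numerical size is unknown; under the assumptions shown, the chance of a significant change without any heat effect runs from 5% to about 75%. The choice of a single-arm pilot is not itself an error. The defect is a causal reading with no stated limit, which should be corrected before results are interpreted.

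**What to change.** **Wording changes (recommended):**

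- In the section on oxygen consumption measurements, say that the 24-48 hour wait reduces acute immersion effects but does not establish that a remaining change is caused by heat.
- In the Study Aim and Objectives sections, say that the pilot estimates the before-to-after change in VO2 with its confidence interval, that this change will not by itself be attributed to heat therapy, and that it serves to plan a controlled study. Name familiarity, effort and drift as the explanations the design leaves open.

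The cost is text and a more modest claim. Participants, visits and measurements are unchanged.

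**Delayed start (optional only):** randomising the same 20 to immediate or delayed start would give a direct estimate of the repeat-test effect. It needs a randomisation procedure, 10 extra T1-type visits and about two more weeks for half the participants. The estimate would be imprecise, and expectation would remain, since delayed participants know they have not yet been heated. The sponsor may reasonably decline it. How a later heart-failure trial is controlled is for that trial's own protocol.
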